#### 15/37

CONFIDENTIAL - HeartGuide BP LVMI Study Protocol - Version 1.0, 09 December 2020 - EDGE 132948; IRAS 280191

- The Cardio-Ankle Vascular Index (CAVI) will be measured non-invasively (see below)
- The participant will then be trained in the use of the HeartGuide watch BP monitor (see below). After completion of training, study participants will be issued with the HeartGuide watch BP monitor and an event diary.
- The second study visit and third study visit for the cMRI scan will be scheduled.

No blood, urine or tissue samples will be collected for this study.

#### Visit 2:

ÎIII

This visit will ideally take place 7 days after visit 1

- Participants will return the HeartGuide BP watch and event diary
- The quality of the HeartGuide watch BP data will be reviewed to ensure that there is a minimum of 3 days of valid HeartGuide watch BP measurements. A minimum of 70% of successful HeartGuide readings will be required for a valid session. Individuals with insufficient BP data will be offered to have the HeartGuide measurement repeated.
- Seated office BP measurements will be recorded
- A 24-hour ABPM monitor will be applied and event diary issued.
- The cMRI booking will be confirmed

#### Visit 3:

- The ABPM and event diary will be returned and the quality of BP measurements reviewed – this can be scheduled to coincide with the cMRI or alternatively, the ABPM device can be returned after 24 hours by courier and visit 3 is then solely devoted to cMRI at patient convenience but within 1 month from visit 1
- The cMRI will be performed

# Figure 1. Study design

# Table 1. Summary of study visits and procedures

Study Procedures	Visit 1	Visit 2	Visit 3
Informed Consent	х		
Demographics and Medical History	х		
Height and weight	х		
Seated blood pressure measurement	х	х	
Heart rate	х		
12-lead ECG	х		
Cardio-Vascular Ankle Index (CAVI)	х		
Issue HeartGuide watch BP monitor	х		
Schedule visit 2 and cardiac MRI	х		
Review quality of HeartGuide data		х	
Issue 24-hour ABPM monitor		х	
Cardiac MRI			х

#### **Detailed Study Processes and Measurements**

#### Seated Clinic blood pressure measurement:

IIIII

Brachial clinic BP will be measured at the heart level over the upper arm with a suitably sized cuff, using a validated oscillometric monitor (HEM-907, Omron Healthcare Co. Ltd., Kyoto, Japan). Measurements will be taken with participants seated in a comfortable position with their arm supported at the level of the heart, legs uncrossed with feet flat on the floor. Measurements will be taken with the study staff in attendance. The BP monitor has an in-built timed protocol to standardise BP measurement. Once initiated, the participant will sit while the monitor counts down for 5 minutes, afterwards a pre-set protocol of 3 consecutive BP measurements spaced by 1 minute is started. Brachial systolic, diastolic and pulse are displayed by the device. BP measurements will be carried out on both arms and the mean of the last two blood pressures on the arm with the highest systolic BP will recorded as clinic BP. Data will be manually entered into the electronic data base.

#### HeartGuide watch BP measurement:

Participants will be provided with the HeartGuide watch BP monitor (figure 2). This is a CEmarked and validated BP monitor. Study participants will be shown how to operate and accurately apply this device to their wrist, charge the device, and use it to take accurate BP measurements. The watch will be worn on the non-dominant wrist.

Figure 2, The HeartGuide BP watch device: a) display; b) start/stop button; c) forward button; d) home button; e) strap/band; f) charging port; g) cuff.

During study visit 1, participants will be briefed on what procedures need to be followed to acquire accurate BP readings including:

- Place the watch ~2.5 cm below the distal wrist crease
- Select the appropriate tightness of the watch using the manufacturer's guide
- Ensure that the watch is positioned in the centre of the wrist with help of the positioning mark located on the watch

For each measurement, the participant will be asked to keep the palm of the non-dominant arm in a neutral position, facing flat against the chest, keeping the watch away from the body and maintaining the centre of the palm still, at heart level. To minimise tension in the watch-wearing non-dominant arm, it should be supported using a tabletop or other solid surface whilst a measurement is being taken. Alternatively, the elbow of the non-dominant arm can be supported using the dominant arm if a supporting surface is not available e.g. whilst standing

(figure3).

# Figure 3, Illustration of correct arm positioning for manually initiated HeartGuide BP measurements; A) with arm supported or B) arm rested on a solid surface.

All measurements will be manually initiated. In the morning after waking and in the evening before going to bed at which two measurements will be taken whilst seated, one minute apart, and following 5 minutes rest, mimicking the protocol for home BP measurement. Participants will also be asked to take single readings (whilst ambulant) at fixed time points during the day (10:00hrs, 12:00hrs, 14:00hrs, 16:00hrs, 18:00hrs), mimicking ambulatory blood pressure

measurement. Individual measurements can also be initiated at any other time point during the day (up to 5 times) and the reason for the additional readings should be recorded in the event diary.

Participants will be asked to take BP measurements using this procedure, for a minimum of 3 week days and up to a maximum of 7 days. The device will store up to a maximum of 100 measurements over the entire monitoring period, which is sufficient for the recommended monitoring schedule over a total of 7 days. To prevent damage to the watch, participants will be required to remove the watch when sleeping or when bathing. In addition, participants will be requested to selectively record their behavior, emotion, and location at the timing of each measurement.

The quality of the HeartGuide watch BP data will be reviewed at visit 2 to ensure that there is a minimum of 3 days of valid HeartGuide watch BP measurements. A minimum of 70% of successful HeartGuide readings will be required for a valid session. Individuals with insufficient BP data will be offered to have the HeartGuide measurement repeated.

#### 24 hour Ambulatory Blood pressure measurement:

Ambulatory blood pressure measurement will be carried out using a validated oscillometric monitor (TM-2441, A&D Co. Ltd., Tokyo, Japan). Participants will be provided-with a suitably sized cuff to be worn on the non-dominant arm and ambulatory measurements will be collected over a maximum of 24 hours on a weekday. Individual measurements will be taken at 30 and 60-minute intervals during waking and sleeping hours, respectively. Participants will be instructed to keep their arm stable and in a relaxed position during each BP measurement. A diary will be provided to the participants to note any changes in activity and to record the time of going to sleep and waking for the period of monitoring. Upon returning the monitor to the study site, the BP data will be downloaded to a study-dedicated laptop and analysed for 24-hour, waking and sleeping BP averages using proprietary software. A minimum of 14 successful waking readings or  $\geq$  70% overall readings will be accepted for analysis. If sufficient readings are not obtained for the analysis, participants will be offered to undergo another 24-hour ABPM measurement.

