Recently a wristwatch style monitor was developed for the measurement of out of office BP (HeartGuide, Omron, Japan). This is smaller, lighter and less intrusive than conventional ABPM monitors and does not depend on an upper arm cuff. Instead, the cuff is incorporated in the strap of the watch (see fig. 2) which allows the patient to activate self-measurement of their BP multiple times during the day, either whilst seated (e.g. similar to HBPM) or when ambulant (similar to ABPM). The device prompts the user via a short vibration at the wrist, to position their wrist at heart level, immediately prior to BP measurement. In a recent study, we showed that BP measured with this device correlated very well with BP measurements using upper-arm cuff-based ABPM when BP was recorded by the HeartGuide watch immediately after each activation of ABPM BP measurement. The present study will extend these findings and evaluate whether average systolic BP measured using the HeartGuide watch is correlated with left ventricular mass index (LVMI) and a comparison of the strength of that correlation with that observed for 24-hour ABPM mean systolic BP and seated office clinic systolic BP. LVMI is the main outcome measure because hypertrophy of the left ventricle is a validated biomarker of elevated pressure and is itself potently correlated with increased risk of adverse cardiovascular outcomes and mortality. The study will use cardiac MRI (cMRI) to measure LVMI because cMRI is recognised as the most accurate and reproducible means of measuring LVMI.

In addition to the measurement of LVMI as the primary outcome, this study will also examine the relationship between different BP parameters and vascular biomarkers of hypertensive injury using the non-invasive measurement of the Cardio-Ankle Vascular Index (CAVI).

The findings of this study will provide evidence of the validity of HeartGuide watch BP measurements when compared with conventional upper arm cuff-based BP measurements and for the first time evaluate the relationship between these various BP measurement techniques and markers of hypertension-mediated organ damage, specifically LVMI. These findings will be important to help define whether the HeartGuide watch BP monitor can provide an alternative means to characterise BP levels for the diagnosis of hypertension and monitoring the response of patients to antihypertensive therapy.

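### The ABPM acceptance rule sets no minimum for sleep readings, so a recording with no night data passes, triggers no repeat, and supplies a 24-hour mean that is really a waking mean

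*Protocol*

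**What the plan says.** All of the ABPM rules stand in the Protocol section on 24-hour ambulatory blood pressure measurement.

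- **Schedule:** "Individual measurements will be taken at 30 and 60-minute intervals during waking and sleeping hours, respectively".
- **Length:** "ambulatory measurements will be collected over a maximum of 24 hours on a weekday". No minimum wear time is given.
- **Acceptance:** "A minimum of 14 successful waking readings or" at least "70% overall readings will be accepted for analysis". The two limbs are alternatives, and neither mentions sleep readings.
- **Repeat:** another recording is offered only if the first falls short of what the analysis needs, so the acceptance rule also decides who is asked to repeat.
- **Averages:** recordings are "analysed for 24-hour, waking and sleeping BP averages using proprietary software". The weighting is not stated. Participants note their sleep and wake times in a diary.

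The Background section says the watch-LVMI correlation will be set against those of the other methods: "a comparison of the strength of that correlation with that observed for 24-hour ABPM mean systolic BP and seated office clinic systolic BP". The section on HeartGuide measurement says that "participants will be required to remove the watch when sleeping or when bathing", so the watch yields daytime data only.

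**The concern.** A 24-hour mean is a defined quantity only if both parts of the day contribute to it. The rule guards the waking part with a count and the whole with a percentage, but leaves the sleeping part unguarded. Participants who take the cuff off at bedtime would be analysed beside those with a full night, under the same variable name.

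This goes beyond detail that a later analysis plan could supply. Because the same rule triggers the repeat, a participant with no night readings counts as sufficient and is not asked back. An analysis plan could exclude that record from the 24-hour mean, but it could not recover the missing night.

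At stake is the secondary comparison of watch, ABPM and office pressure as correlates of LVMI, together with any analysis that uses the sleeping mean.

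**Working it through.** **The plan's own figures.** The protocol gives the 14-reading and 70% thresholds without derivation, so there is nothing to reproduce for them. Its power figures do reproduce by Fisher's z: Φ(atanh(0.30) × √47 − 1.96) = 0.564 against the stated 0.56. They concern the watch-LVMI correlation and do not depend on ABPM acceptance.

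**Inputs.** From the protocol: 2 readings per hour awake, 1 per hour asleep, up to 24 hours, and the two limbs. Assumed, because the protocol gives no figures: sleep of S = 8 hours (other values shown) and a systolic sleep dip d of 10 to 20 mmHg.

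**Step 1: the schedule.** Waking readings = 2(24 − S), sleeping readings = S, total = 48 − S. At S = 8 this is 32 + 8 = 40.

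**Step 2: what the 70% limb adds.** The limb needs 0.7(48 − S) readings. The fewest waking readings that can satisfy it, with every sleep reading successful, is 0.7(48 − S) − S = 33.6 − 1.7S. At S = 8 this is 28 − 8 = 20, so the 14-waking limb is already met. It stays at 14 or more for S up to 19.6/1.7 = 11.5 hours. Counting whole readings, the minimum is 14 at 12 hours and 12 at 13 hours.

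For shortened recordings, suppose the 70% is taken of attempted readings and 8 hours of sleep are included:

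| Wear (h) | Readings | 70% needed | Fewest waking |
|---|---|---|---|
| 24 | 40 | 28 | 20 |
| 20 | 32 | 23 | 15 |
| 19 | 30 | 21 | 13 |

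The 70% limb therefore admits extra records only with sleep beyond about 12 hours or recordings of about 19 hours or less.

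**Step 3: the effective threshold.** 14/40 = 35% of all scheduled readings, 14/32 = 44% of waking readings, and 14 × 0.5 = 7 hours of recording. For 5 to 10 hours of sleep the share of all readings is 14/43 = 33% to 14/38 = 37%.

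**Step 4: no night needed.** The first limb counts waking readings only. The second can also be met without sleep: 28 are needed and 32 waking readings are scheduled. Deleting the 14-reading limb would therefore not cure the problem.

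**Step 5: size in one record.** With waking mean W and sleeping mean W − d, the time-weighted 24-hour mean is W − d × S/24. A record without sleep readings gives W, which is too high by d × 8/24 = d/3:

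- d = 10: 3.3 mmHg
- d = 15: 5.0 mmHg
- d = 20: 6.7 mmHg

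If the software instead takes a plain mean of readings, the gap from a complete record is d × 8/40: 2.0, 3.0 and 4.0 mmHg.

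**Step 6: size in the correlation.** A shift shared by everyone leaves Pearson's r unchanged; only differences between participants matter. As an illustration, let a fraction p of records lack the night, unrelated to pressure or LVMI, with a common shift δ. Then r is multiplied by SD/√(SD² + p(1 − p)δ²). Take the least favourable p = 0.5, an assumed SD of 12 mmHg, and the protocol's r of 0.30 for 24-hour ABPM and LVMI:

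- δ = 3.3: 0.30 × √(144/146.8) = 0.297
- δ = 6.7: 0.30 × √(144/155.1) = 0.289

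This is not a bound. Dips vary between people, and those who remove the cuff may differ from those who keep it on.

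**The case against.** The strongest reply is that this is a narrow matter in a secondary analysis, that accepting a record for analysis does not say for which average, and that one clarifying sentence would settle it. The narrowness stands: neither the primary outcome nor the power calculation uses ABPM. The clarification would settle which records enter which mean, but not the repeat offer, which depends on the same rule at the time of data collection.

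A reader might infer more than the documents support:

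- **That the 70% limb is always idle.** It is idle for full recordings with ordinary sleep. The protocol makes 24 hours a maximum, and short recordings or very long sleep can bring the limb into play.
- **That half-hourly and hourly sampling over-weights waking pressure.** At 8 hours of sleep, waking supplies 80% of readings and 67% of the time, but this distorts the mean only if the software averages readings without weights. The weighting is unstated, not shown to be wrong.
- **That comparing the watch with ABPM builds in a false device bias.** The Background section names the 24-hour mean for comparing correlations. The Secondary Outcomes section fixes no 24-hour comparator for the t-tests or Bland-Altman plots, and a waking ABPM mean is already derived. Daytime-only watch data are a declared feature: the Background section says the watch gives a different profile from ABPM.
- **That several mmHg of overstatement must spoil the correlation.** A uniform shift does nothing to r; the harm depends on how many records lack the night and how they differ.

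**Conclusion.** The point holds for the acceptance rule. With a full recording and about 8 hours of sleep, the written rule amounts to 14 waking readings, 35% of the schedule, with no night data required. A record without sleep readings passes, prompts no repeat, has no sleeping mean, and overstates a time-weighted 24-hour mean by d/3, or 3.3 to 6.7 mmHg for assumed dips of 10 to 20 mmHg.

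The result is uneven error in the 24-hour mean that serves as comparator for the LVMI correlation. The protocol does not say how many of the 50 records would be affected, and in the simple illustration the loss in r is small. The case for change is that the index would not mean the same thing in every participant, that the missing night cannot be recovered later, and that correction is cheap. It does not rest on any threat to the primary result.

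**What to change.** Set the acceptance criterion separately for the waking and sleeping periods, with the periods taken from the diary; for example, 70% of scheduled readings in each. At 8 hours of sleep that is 23 of 32 waking (22.4 rounded up) and 6 of 8 sleeping (5.6 rounded up). The exact thresholds are for the team to choose; the essential change is that sleep has its own minimum. Then state that:

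1. a record enters the 24-hour and sleeping means only if both periods pass;
2. a record that passes only the waking criterion contributes the waking mean alone;
3. failing the sleep criterion triggers the repeat recording already offered.

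**Cost:** a few lines of wording and code, and a few records lost from the 24-hour index or a few repeat recordings. A 70% waking criterion would also be stricter than the present 14 readings, so some records that now pass on daytime data would fail.

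Two clarifications would help, though neither corrects an error: state that the 24-hour mean is time-weighted, and name the waking ABPM mean as the matched comparator for the watch in difference and Bland-Altman analyses, since the watch is off during sleep. The 24-hour mean can remain the comparator for the LVMI correlation.

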#### **12-lead Electrocardiogram:**

Study participants will lay supine for ~5 minutes prior to undergoing a 12-lead ECG (ASSY CAM-14 version 2; GE Medical Systems Information Technologies Inc., Wauwatosa, WI, USA). Data will be collected and sorted on the study-dedicated laptop using the GE Medical Systems Cardiosoft software (Cardiosoft version 6.73; GE Healthcare, Chicago, IL, USA).

#### Anthropometrics – height and weight:

Height and weight will be recorded using a stadiometer (Seca 274, Seca, Birmingham, UK) with electronic data capture. Participants will be asked to remove shoes for height and weight measurements.

#### Cardio-Ankle Vascular Index (CAVI):

Non-invasive assessment of arterial stiffness will be completed using the Cardio-ankle vascular index device (VS1500N, Fukuda Denshi, Tokyo, Japan). This device measures BP using cuffs placed over the upper arm and ankles, cardiac sounds using a phonograph placed on the sternum and a 2-lead ECG to gate readings. Vascular length is computed from body surface area and is used with pulse transit time from the aorta to ankle to derive pulse wave velocity. CAVI is computed by the device and is a scaled transformation of heart-ankle pulse wave velocity and is a surrogate of large artery stiffness. Participants will be instructed to relax and lie supine for ~2 minutes to ensure heart sounds are detectable and ECG recordings are stable before measurements are taken. Two measurements will be taken consecutively with ~1 minute between measurements.

#### Cardiac MRI scan acquisition and analysis:

Cardiac MRI scans will be conducted at the Chenies Mews Imaging Centre. All scans will be performed on a 1.5T scanner (Magnetom Aera, Siemens Medical Solutions, Erlangen, Germany). Imaging of the heart will use an accelerated steady-state free precession protocol. Contrast will not be used in any imaging for this study. MRI scans will be conducted using standard NHS diagnostic and safety procedures.

Analysis of left ventricular (LV) mass will be undertaken using standard imaging software. The stack of LV images will be segmented to define the endocardial and epicardial borders. Summation of each individual slice will be calculated to determine LV mass. MRI scans will be **22/37** CONFIDENTIAL - HeartGuide BP LVMI Study Protocol - Version 1.0, 09 December 2020 - EDGE 132948; IRAS 280191

pseudo-anonymised so observers are not able to link any patient level data during analysis. MRI data will be manually entered into the study database. LV mass will be indexed to body surface area to derive the LVMI. For secondary outcomes additional MRI indices will be acquired, including cardiac volumes, functional parameters and aortic flow.

# **Statistical Analysis Plan and Data Analysis**

#### Primary Outcome analysis and Sample size estimation

The primary outcome is the association between mean "out of office" systolic BP measured by the HeartGuide watch BP monitor and LVMI measured by cMRI. This relationship will be assessed by Pearson's correlation coefficient for normally distributed data. For the primary outcome, based on 50 cases, using an estimated Pearson's correlation coefficient of 0.30, using data on the relationship between 24-hour ABPM and cMRI LVMI from our prior studies, the power would be 0.56 at P = 0.05. With 50 cases and a correlation coefficient of 0.40, the power would be 0.83 at P = 0.05. For the full analysis with 100 cases (merged analysis with the Jichi Medical University study data), at a correlation coefficient of 0.30, the power is 0.86, and a correlation coefficient of 0.40, the power is 0.99 at P = 0.05.

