An interesting aspect of the study is that the measurement of BP with the HeartGuide watch BP monitor will be used to measure BP whilst rested and seated in the morning and evening, thereby mimicking the usual pattern of BP measurement recommended in guidelines for HBPM with a conventional upper-arm cuff-based device. However, the HeartGuide watch BP monitor also allows for BP measurements to be taken at other multiple times during the day. This is similar to the profile of BP measurements taken by ABPM but, with measurements over multiple days unlike ABPM which typically only measures BP over a single day. In this regard, the HeartGuide watch BP monitor will provide a different profile of BP measurement when compared to conventional HBPM or ABPM. It is a key additional objective of this study to define whether this new profile of BP measurement reveals any difference in the strength of the correlation between BP and LVMI.

This protocol describes the UK based study. A similar protocol will be used for a parallel study of similar size and design, developed with our collaborators at the Jichi Medical University in Japan. The plan is to evaluate the data from both studies independently but also combine the results of both studies to evaluate the relationship between BP measurement methods and indices and LVMI in different population cohorts representing Europe and Asia.

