# **Study Design**

This is a single centre cross-sectional study in 50 people with elevated systolic BP i.e.  $\geq$  130 mmHg, or receiving antihypertensive therapy. The study evaluates the relationships between BP measured with different validated and CE-marked devices, used for their intended purpose, and LVMI, measured by cMRI. The study does not involve any treatments or interventions.

A parallel study of similar design and purpose is also planned to be undertaken Jichi Medical University, Tochigi, Japan. This will allow for comparison of BP relationships with LVMI across two different population cohorts. To facilitate this two-centre analysis, non-identifiable data from both studies will be merged.

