#### 23/37

CONFIDENTIAL - HeartGuide BP LVMI Study Protocol - Version 1.0, 09 December 2020 - EDGE 132948; IRAS 280191

- The HeartGuide Watch BP monitor
- b. ABPM
- c. Seated clinic BP
- 4. Relationship between CAVI indices and MRI parameters including;
  - a. LVMI/unindexed LV mass
  - b. Cardiac volumes
  - c. Indices of vascular structure/function
- 5. Relationships and any significant differences between various BP indices measured by:
  - a. The HeartGuide Watch BP monitor
  - b. ABPM
  - c. Seated clinic BP

All data will be analysed for distribution pattern and tested using appropriate methods. Summary statistics for continuous variables will be reported as means and standard deviation or 95% confidence intervals where appropriate. Categorical variables will be reported as n and percentage. Analysis of secondary outcomes will use similar techniques as used for the primary outcome i.e. Pearson's correlation coefficient calculated for the relationships between various BP parameters and cMRI measurements of LV mass, CAVI measurements or ECG voltage criteria for LV mass. The relationship between cMRI parameters and CAVI indices will also be determined using Pearson's correlation coefficient. Additionally, regression coefficients for all relationships will be calculated using linear regression models. Fisher's r to z transformation will be used to compare correlation coefficients between BP modes and MRI or CAVI or ECG-derived parameters. Direct comparison of BP indices will use student's t-tests, one-way ANOVA or other appropriate tests for non-normally distributed data. Data will also be plotted using Bland-Altman plots. Data may also be adjusted for potentially confounding demographic and anthropometric parameters where appropriate. A two-sided significance level of  $P \leq 0.05$  will denote statistical significance. Effect size will also be reported. Due to the relatively small sample size, it is not anticipated that any sensitivity analyses will be carried out.

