#### Data management

Personal data will be collected as part of this study and will be stored in a secure data environment at UCL (Data Safe Haven, DSH) and will only be accessible to study team members and authorised regulatory authorities. Stored personal data will only include participants' contact details (needed to book appointments and tests), their emergency contact details (needed in case of an emergency), their GP details (needed to inform the GPs about any relevant results and incidental findings) and signed and dated informed consent forms. All other study data will be pseudo-anonymised and stored electronically using a customised electronic database (Research Electronic Data Capture (REDCap)) or on proprietary systems required for device data collection e.g. computers linked to the MRI scanner. The key to the pseudoanonymised data will be stored in the UCL secure data environment (DSH). Pseudo-anonymised data from the REDCap database will be exported to statistical analysis systems (STATA, R-Studio) for processing and analysis. Pseudo-anonymised processed data from statistical analysis systems will be shared with collaborative investigators undertaking a similar parallel study at Jichi Medical University, Tochigi, Japan or with the study funder, Omron Healthcare Co. Ltd. Any data shared with collaborators or other investigators will be pseudo-anonymised and only include research results after statistical processing, and will not include personally identifiable information.

All study investigators and trial site staff will comply with the requirements of the General Data Protection Regulation (GDPR) and Data Protection Act 2018 with regards to the collection, storage, processing and disclosure of personal information. Study staff will safeguard the privacy of participants' personal data.

Personal data will be retained for up to one year following trial completion after which time it will be destroyed securely. All other non-identifiable data will be retained for up to ten years following trial completion after which time it will be archived according to standard UCL/UCLH procedures.

The study Chief Investigator will act as data custodian.

# 

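### The merged UK–Japan correlation is specified without a centre term, so differences between the centres in mean systolic BP and mean LVMI would bias the pooled r

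*Protocol*

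**What the plan says.** - **Method.** Under Primary Outcome analysis and Sample size estimation, one method is given for the association between HeartGuide systolic BP and LVMI: "This relationship will be assessed by Pearson's correlation coefficient for normally distributed data".
- **Power, UK alone.** With 50 cases and r = 0.30, "the power would be 0.56 at P = 0.05". At r = 0.40 it is 0.83.
- **Power, merged.** The combined calculation is introduced with "For the full analysis with 100 cases (merged analysis with the Jichi Medical University study data), at a correlation coefficient of 0.30". For that r the protocol gives 0.86; for r = 0.40 it gives 0.99.
- **Merging.** Study Design: "To facilitate this two-centre analysis, non-identifiable data from both studies will be merged". Background and Purpose of the Study says the plan is to "evaluate the data from both studies independently but also combine the results of both studies", and describes the two cohorts as different populations, European and Asian. The Japanese study is said to follow a similar protocol and to be of similar size.
- **Adjustment.** The text under Secondary Outcomes adds linear regression for all relationships and permits, without requiring, adjustment for demographic and anthropometric confounders. Centre is not named. The same text sets a two-sided 0.05 level and expects no sensitivity analyses.

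**The concern.** A Pearson correlation over two merged groups measures two things at once: how LVMI varies with BP among people in the same centre, and whether the centre with the higher mean BP also has the higher mean LVMI. Only the first is the study question. The second can reflect population, recruitment, treatment or measurement differences that have nothing to do with whether the watch reading tracks LV mass.

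The merged analysis carries weight. At r = 0.30, the value the protocol takes from prior data, the UK study alone has power 0.56. Only the merged analysis reaches a conventional level of power at that r. If it is run as written, it could reject with no association in either country, or miss an association of the planned size that is present in both.

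**Working it through.** **Inputs from the protocol.** n = 50 (UK) and n = 100 (merged), r = 0.30 and 0.40, two-sided alpha 0.05. I take 50 per centre (100 − 50 = 50, consistent with a parallel study of similar size).

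**Assumed inputs.** Differences between centre means, dx for systolic BP and dy for LVMI, in within-centre SD units. The protocol gives none, so I use 0 to 1 SD. I also assume a common within-centre r and equal SDs in the two centres.

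**Step 1: the protocol's own figures.** Power = Φ(atanh(r)·√(n−3) − 1.96), plus a negligible opposite tail. With atanh(0.30) = 0.3095 and atanh(0.40) = 0.4236:

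| n | r | Computed | Stated |
|---|---|---|---|
| 50 | 0.30 | 0.564 | 0.56 |
| 50 | 0.40 | 0.828 | 0.83 |
| 100 | 0.30 | 0.862 | 0.86 |
| 100 | 0.40 | 0.987 | 0.99 |

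All four reproduce. The arithmetic is sound.

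**Step 2: what the pooled correlation estimates.** For two equal centres, the centre means add dx·dy/4 to the covariance, and dx²/4 and dy²/4 to the variances:

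pooled r = (r + dx·dy/4) / √[(1 + dx²/4)(1 + dy²/4)]

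Example, r = 0 and 0.8 SD in both: 0.16/1.16 = 0.138; atanh = 0.1388; × √97 = 1.367; Φ(1.367 − 1.96) ≈ 0.28.

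Example, r = 0.30 and 0.8 SD in opposite directions: (0.30 − 0.16)/1.16 = 0.121; atanh = 0.1213; × √97 = 1.194; Φ(1.194 − 1.96) ≈ 0.22.

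| Shift in both variables | r = 0, same direction: pooled r | Rejection rate | r = 0.30, opposite directions: pooled r | Power |
|---|---|---|---|---|
| 0 | 0.00 | 0.05 | 0.30 | 0.86 |
| 0.25 SD | 0.015 | 0.053 | 0.28 | 0.81 |
| 0.5 SD | 0.06 | 0.09 | 0.22 | 0.61 |
| 0.8 SD | 0.14 | 0.28 | 0.12 | 0.22 |
| 1.0 SD | 0.20 | 0.51 | 0.04 | 0.07 |

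Same-direction shifts with a true r of 0.30 inflate the pooled r, to 0.34 at 0.5 SD and 0.44 at 1.0 SD. A shift in one variable alone creates no false association; 1 SD in LVMI only lowers r to 0.30/√1.25 = 0.27 and power to 0.77.

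Simulation (50 per centre, 40,000 replicates) agrees. The null rejection rate was 0.088 at 0.5 SD and 0.525 at 1.0 SD; power with opposite shifts was 0.61 and 0.056.

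**Step 3: with a centre term.** The partial correlation uses n − 4 = 96. Power is Φ(0.3095·√96 − 1.96) = 0.858 at r = 0.30 and 0.986 at r = 0.40. In the same simulations, type I error stayed at 0.048–0.051 and power at 0.860–0.865 whatever the shift. Two-stage pooling of Fisher z has variance 1/(47 + 47) = 1/94 and gives 0.851 and 0.984.

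**The case against.** The strongest reply is that this is an omission and not a decision to ignore centre. The plan to combine results is compatible with a two-stage method, regression is promised for all relationships, confounder adjustment is allowed, and a separate SAP could add centre. That is fair, and the point should not be put as an explicit exclusion of centre. But the protocol itself fixes the primary method and powers the merged sample. Its adjustment clause is optional and names other variables. Followed as written, it yields the unadjusted pooled r.

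Second, the size depends on unknown centre differences. This stands: the effect is small at 0.25 SD, and serious distortion needs sizeable shifts in both variables. Indexing LV mass to body surface area deals with part of any body-size difference. The UK-only analysis is untouched. Separate country analyses would help expose an artefact, although at r = 0.30 and n = 50 each has power of only about 0.56.

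Three stronger readings are tempting and not supported:

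- **That the stated power proves naive pooling.** It does not. The centre-adjusted figures, 0.858 and 0.986, round to the same 0.86 and 0.99.
- **That Data management forbids the merge.** The restriction that shared data "only include research results after statistical processing" governs what goes out to collaborators. The Trial Summary places the analysis at University College London, so receiving Japanese records there would not breach it.
- **That testing UK and merged data each at 0.05 inflates the family-wise error by a calculable amount.** Any such figure needs a rule that either result alone counts as success. The protocol states no such rule.

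**Conclusion.** The concern holds as a fault in how the merged analysis is specified, not in the power arithmetic. The 0.86 and 0.99 are correct for a single homogeneous population, or for a within-centre r with centre adjusted. They do not describe an unadjusted correlation over two populations whose means differ in both variables.

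Over the assumed range, false-positive rates run from about 5% (0.25 SD) to 51% (1.0 SD). Power at a within-centre r of 0.30 falls to about 0.81 (0.25 SD) and 0.22 (0.8 SD) when the shifts are opposite. These figures rest on equal centres of 50, a common within-centre r and equal SDs. They illustrate what could happen and do not predict what these two cohorts will show. Because adjustment costs almost nothing, there is no reason to leave the result exposed.

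**What to change.** In Primary Outcome analysis and Sample size estimation, define the merged analysis as either the centre-adjusted (partial) correlation between HeartGuide systolic BP and LVMI, or a regression of LVMI on HeartGuide systolic BP with a centre term. Add a BP-by-centre check of heterogeneity, reported with its interval. With 50 per centre, the difference in Fisher z has a standard error of √(2/47) = 0.21, so this check is descriptive.

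Keep the stated 0.86 and 0.99, and say that they refer to the within-centre correlation. If two-stage pooling of Fisher z with weights n − 3 is preferred, state 0.85 and 0.98 instead.

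The cost is a change of wording before the data are merged: no extra participants or measurements, and a loss of power of less than half a percentage point (0.862 to 0.858), or about one point with the two-stage version.
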